# 8.1.5 Pregnancy

Pregnancy itself is not regarded as an AE unless there is a suspicion that the IMP has interfered with a contraceptive method. If pregnancy occurs during the study, the outcome of the pregnancy will then need to be collected poststudy

Information regarding pregnancies must be collected on the AE page of the eCRF and reported to the sponsor as an SAE. The sponsor will request further information from the investigator as to the course and outcome of the pregnancy using the Standard Pregnancy Outcome Report Form.

The investigator must instruct all female subjects to inform them immediately should they become pregnant during the study. The investigator should counsel the subject, discuss the risks of continuing with the pregnancy and the possible effects on the foetus. Monitoring of the subject should continue until conclusion of the pregnancy, which may involve follow-up after the subject's participation in the study has ended.

#### 8.1.6 *Deaths*

All AEs resulting in death during the study period must be reported as an SAE within 24 hours of the investigator's knowledge of the event.

The convention for recording death is as follows:

- AE term: lead cause of death ([e.g. multiple organ failure, pneumonia, myocardial infarction]),
- Outcome: fatal.

The **only exception** is if the cause of death is unknown (i.e. sudden or unexplained death), in which case the AE term may be "death" or "sudden death".

# 8.1.7 Discontinuation/Withdrawal due to Adverse Events/Serious Adverse Events

Discontinuation/withdrawal due to AEs should be distinguished from discontinuation/withdrawal due to insufficient response to the IMP (see Section 4.3).

If the IMP or comparator is discontinued due to an SAE, it must be reported immediately to the sponsor's designated representative (see Section 8.1.4).

In all cases, the investigator must ensure the subject receives appropriate medical follow-up (see Section 8.1.3).

#### 8.1.8 Reporting to Competent Authorities/IECs/IRBs/Other investigators

The sponsor will ensure that processes are in place for submission of reports of Suspected Unexpected Serious Adverse Reactions (SUSARs) occurring during the study to the CA, IECs

**PAGE 53/103** 

and other investigators concerned by the IMP. Reporting will be done in accordance with the applicable regulatory requirements.

#### 8.2 Clinical Laboratory Tests

Blood for clinical local laboratory tests will be collected at Visits 1, 2 and 4 for local laboratory. At Visit 1: haematology and biochemistry.

At Visit 2 (during anaesthesia) and Visit 4 or early withdrawal visit: blood biochemistry.

Blood will be also collected at Visits 1, 2 and 4 for central laboratory serum sulphate testing.

Urinary sampling will be performed for local laboratory at Visits 1, 2 and 4 (or early withdrawal visit).

Additional urinary sample will be performed at Visits 1, 2 and 4 for sulphate dosage by central laboratory.

The investigator will review the safety laboratory test results, document the review and record any clinically relevant changes occurring or observed during the study in the AE section of the eCRF (see Section 8.1.2.4 for abnormal laboratory tests that should be recorded as AEs).

All clinically relevant abnormal laboratory tests occurring during the study will be repeated at appropriate intervals until they return to Baseline or to a level deemed acceptable by the investigator and the sponsor's clinical monitor (or his/her designated representative) or until the abnormality is explained by an appropriate diagnosis.

# 8.2.1 Haematology

Blood samples (3 mL) will be collected (in a potassium ethylene diamine tetra acetic acid (EDTA) tube) to assess the following parameters: CBC: red blood cell (RBC) count, haemoglobin, haematocrit, mean corpuscular volume (MCV), mean corpuscular haemoglobin (MCH), mean corpuscular haemoglobin concentration (MCHC), white blood cell (WBC) count with differential (nutrophils, lymphocytes, monocytes, eosinophils, basophils, and others), platelet count and international normalised ratio (INR).

# 8.2.2 Blood Biochemistry

Blood samples (2.5 mL) will be collected (in an activator gel tube) to assess the following parameters by local laboratory:

Anion gap, ALT, AST, CPK, LDH, GGT, total and conjugated bilirubin, creatinine, urea, serum electrolytes (sodium, potassium, chloride, calcium, magnesium, phosphorus, bicarbonate), alkaline phosphatase, albumin, total protein, CRP, uric acid, INR, creatinine clearance (calculated GFR), osmolality

Blood samples (2 mL) will be collected for sulphate level dosage by central laboratory at Visits 1: Baseline/treatment Visit 2: Colonoscopy and Visit 4: end of study or early withdrawal study.

All the data will be reported in the eCRF by single data entry and monitored during on site visits.

# 8.2.3 Urinalysis

Fresh urine samples (at least 10 mL) will be collected to assess the following parameters: pH, protein, ketones, bilirubin, blood, urobilinogen, nitrites, leukocytes, glucose and specific gravity by dipstick.

**PAGE 54/103** 

Microscopy will be performed, if indicated, but results will not be collected in the eCRF. Osmolality and ketones will be measured and the results will be reported in the eCRF. If in the opinion of the investigator there are any clinically significant abnormalities in microscopy, they will be recorded as an AE in the eCRF.

# 8.2.4 Pregnancy Test

A blood pregnancy test will be performed for all female subjects of childbearing potential at Visit 1 and if clinically indicated thereafter. Urine pregnancy test will be performed only when blood tests including pregnancy have been performed prior to Visit 1.

Any adolescent female with childbearing potential becoming pregnant during the study will be withdrawn. All pregnancies that occur during the study are to be reported as described in Section 8.1.5.

#### **8.3** Physical Examination

Physical examinations will be conducted at Visit 1 and End of Study (Visit 4) /Early Withdrawal.

Any clinically significant physical examination findings (abnormalities) observed during the study will be reported as AEs. Any physical examination findings (abnormalities) persisting at the end of the study will be followed by the investigator until resolution or until reaching a clinically stable endpoint.

# 8.4 Vital Signs

Blood pressure and HR will be assessed with an automated device so that measurements are independent of the observer. Blood pressure and HR will be recorded in standing position and after 5 minutes rest in supine position at visit 1, after 5 minutes rest in supine position at Visits 2 and 4. Absolute values and change from Baseline will be analysed.

Body temperature and weight will be recorded.

# 8.5 Histological examination of colonic biopsy

Should any macroscopic lesions suspected by the investigator to be induced by colonic lavage, the histological examination of the biopsies will be described and recorded as a TEAE.

# 8.6 Symptom Scale

This scale will be completed by the subject/caregiver at Visit 1, after treatment intake (Table 11). Subjects/caregivers will rate their overall experience of stomach cramping, stomach bloating and nausea on a 5-point scale, with 1=no symptoms, 2=mild, 3=bothersome, 4=distressing and 5=severely distressing symptoms. Symptoms rated from mild (2) to severely distressing (5) must be reported as an AE.

Symptom 1=no symptoms 2=mild 3=bothersome 4=distressing 5=severely distressing

Stomach cramping Stomach bloating Nausea

Table 11 Symptom Scale

PAGE 55/103

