**PAGE 30/103** 

#### 3.2.2.2 Safety and Tolerability Variables

- Collection of AEs (for up to 30 days following the day of colonoscopy)
- Tolerability assessed by a Symptom Scale after each dose of treatment. Subjects will rate their preparation related symptoms after intake (stomach cramping, stomach bloating and nausea) on a paediatric 5-point scale, ranging from 1=no symptoms to 5= severely distressing symptoms
- Description and histological examination of any colonic biopsy specimens of mucosal lesions suspected by the investigator to have been caused by colonic lavage
- Vital signs including body weight and physical examination
- Laboratory data: serum and urinary biochemistry:
  - Visit 1
  - Day 2 (colonoscopy)
  - Visit 4

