**PAGE 35/103** 

#### 4 SELECTION AND WITHDRAWAL OF SUBJECTS

#### 4.1 Inclusion Criteria

Subject MUST satisfy all of the following entry criteria before being allowed to participate in the study:

- (1) Provision of signed ICF to participate in the study obtained from the adolescent's parent(s)/ legal representative and a signed assent form from the adolescent according to local law
- (2) Male or female subjects between 12 to 17 years of age (inclusive)
- (3) Body weight more than 40 kg
- (4) Female of childbearing potential must have a negative pregnancy test
- (5) If female, and of child-bearing potential, subject must use an acceptable form of birth control (hormonal birth control, intrauterine device (IUD), double-barrier method, or depot contraceptive)
- (6) Routinely accepted indication for undergoing colonoscopy, including but not limited to polyposis coli diagnosis or surveillance, gastrointestinal bleeding, unexplained diarrhoea or constipation, surveillance of inflammatory bowel disease or confirmation of mucosal healing, abdominal pain, abnormal endosonography or manometry, anaemia of unknown aetiology, cancer surveillance
- (7) In the investigator's judgment, the parent(s)/legal representative are/is mentally competent to provide informed consent for the subject to participate in the study
- (8) In the investigator's judgement, subject is able and willing to follow study procedures including drug administration and response to questionnaires

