# 8.1.1 Definition of an Adverse Event

An AE is the development of an undesirable medical condition or the deterioration of a preexisting medical condition following or during exposure to a pharmaceutical product, whether or not considered causally related to the product. An undesirable medical condition can be symptoms (e.g. nausea, chest pain), signs (e.g. tachycardia, enlarged liver) or the abnormal results of an investigation (e.g. laboratory findings, electrocardiogram). In clinical studies, an AE can include an undesirable medical condition occurring at any time, including run in or washout periods, even if no IMP has been administered.

This definition includes events occurring from the time of the subject giving informed consent until the end of the study (as defined in Section 3.5).

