3.2.2.1 Adverse events

All AEs will be coded according to MedDRA (last version used for coding during the study course) and will be classified by MedDRA preferred term (PT) and system organ class (SOC). AE listings will be presented by subject, SOC and PT for all AEs, serious AEs (SAEs) and AEs leading to withdrawal on the safety population.

A TEAE is defined as any AE that occurs during the active phase of the study if:

it was not present prior to receiving the first dose of IMP

or

• it was present prior to receiving the first dose of IMP but the intensity increased during the active phase of the study.

All TEAEs will be flagged in the AEs listings.

An overall summary table of all AEs will be presented with the number of AEs and the numbers and percentage of subjects with exact 95 % CI for each of the following categories:

- Any AEs,
- Any SAEs,
- Causality of SAEs,
- Any TEAEs,
- Intensity of TEAEs,
- Causality of TEAEs,
- Causality and intensity of TEAEs,
- Any TEAEs leading to death,
- Any TEAEs leading to withdrawal.

In the event of multiple AEs being reported by the same subject, each subject is counted for each intensity level, each causality level or each intensity and causality combined level. That means that the total number of subjects for all levels of intensity/causality might be higher

than the overall number of subjects with at least one AE. Related adverse events are those events with causality missing or related.

Incidence by SOC/PT of all reported TEAEs, related TEAEs, SAEs and TEAEs leading to withdrawal of study medication will be tabulated by treatment group and overall. In addition, summary tables by SOC/PT will present TEAEs by maximum intensity and drug relationship and will present TEAEs with incidence ≥ 2 %. And a summary table will present TEAEs by decreasing frequency of PT.

In the event of multiple occurrence of the same AE (same PT) being reported by the same subject, the maximum intensity (severe > missing > moderate > mild) and the most serious causality (related > not related) for each concerned PT will be chosen.

Moreover, the summary table will be duplicated by sex, age class and weight class, as well as the summary table of the incidence of TEAEs by SOC and PT.

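### Every post-dose cramping, bloating or nausea score of 2 or more must be reported as an AE, but with no pre-dose score an unchanged background symptom cannot be told reliably from a new or worsened one

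*Protocol*

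**What the plan says.** **Reporting rule.** Protocol 8.6: "Symptoms rated from mild (2) to severely distressing (5) must be reported as an AE". No condition about the subject's state before dosing is attached.

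**Timing.** Protocol 3.2.2.2: "Tolerability assessed by a Symptom Scale after each dose of treatment". Protocol Table 5, the leaflet contents in Protocol 14.2.2 and SAP Table 6 place the scale with Dose 1 and Dose 2 only. The Visit 1 list in Protocol 5.2.2 contains no pre-dose rating.

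**What is rated.** Protocol 3.2.2.2: "Subjects will rate their preparation related symptoms after intake (stomach cramping, stomach bloating and nausea". The synopsis and SAP 1.4.2.2 also tie the rating to the preparation. Protocol 8.6 does not: "Subjects/caregivers will rate their overall experience of stomach cramping, stomach bloating and nausea on a 5-point scale".

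**AE and TEAE.** Protocol 8.1.1: "An AE is the development of an undesirable medical condition or the deterioration of a preexisting medical condition". Under Protocol 10.4.7 and SAP 3.2.2.1 an AE is treatment-emergent if it was absent before the first dose, or if "it was present prior to receiving the first dose of IMP but the intensity increased during the active phase of the study".

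**Population.** The accepted indications in Protocol 4.1 include "surveillance of inflammatory bowel disease or confirmation of mucosal healing, abdominal pain", as well as unexplained diarrhoea and constipation.

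**Analysis.** SAP 3.2.2.4 describes each symptom after each dose, and a three-symptom total, by treatment group. It plans no change from baseline. SAP 3.2.2.2 and 3.2.2.3 do plan change from baseline for biochemistry, sulfates and vital signs.

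**The concern.** Section 8.6 turns a score into an AE without asking whether the symptom is new. A subject who arrives with mild cramping and still has mild cramping after Dose 1 scores 2, and the site must report it. Section 8.1.1 would not call that an AE.

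The TEAE definition is meant to remove such cases. For a symptom already present it needs to know whether intensity rose, and no earlier rating on the same scale exists. The wording in 8.6 makes this worse, because it asks about the whole experience where the other descriptions ask about effects of the preparation.

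Comparing safety and tolerability between arms is a secondary objective. If background symptoms enter the TEAE counts, both arms look less well tolerated than they are and the relative contrast is blurred. The symptom-score tables have no filter of any kind.

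**Working it through.** **1. The passages side by side.** Take a subject with cramping that would score 2 before dosing and scores 2 after Dose 1.

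- Protocol 8.6: report as an AE.
- Protocol 8.1.1: not an AE, because nothing developed or deteriorated.
- Protocol 10.4.7 and SAP 3.2.2.1: not a TEAE, provided someone can show that the symptom was present and did not worsen.

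The evidence for that last step is indirect. Visit 1 records ongoing medical history, the indication for colonoscopy and AEs since consent, but no symptom score. AE intensity has three levels (Protocol 8.1.2.1) and the Symptom Scale has five, with no mapping between them. Where an AE onset date is missing or incomplete, SAP 3.2.3.2 assumes a TEAE unless other data indicate differently.

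**2. Possible size.** The documents give no expected symptom or TEAE rates for this trial and no prevalence of background symptoms, so there is no figure of the plan's own to reproduce. Everything below is assumed.

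Let q be the true treatment-emergent rate in an arm. Let b be the share of subjects with a background symptom that persists at 2 or more and passes unfiltered into the TEAE count. Take b as equal in both arms and independent of the drug effect. Then:

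reported rate = b + (1 − b)q

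reported difference = (1 − b) × true difference

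| True rates | b | Reported rates | Difference (points) | Ratio |
|---|---|---|---|---|
| 30% vs 45% | 0 | 30.0% vs 45.0% | 15.0 | 1.50 |
| | 10% | 37.0% vs 50.5% | 13.5 | 1.36 |
| | 20% | 44.0% vs 56.0% | 12.0 | 1.27 |
| | 30% | 51.0% vs 61.5% | 10.5 | 1.21 |
| 5% vs 15% | 0 | 5.0% vs 15.0% | 10.0 | 3.00 |
| | 10% | 14.5% vs 23.5% | 9.0 | 1.62 |
| | 20% | 24.0% vs 32.0% | 8.0 | 1.33 |
| | 30% | 33.5% vs 40.5% | 7.0 | 1.21 |

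Worked line for 30% vs 45% at b = 20%: 0.20 + 0.80 × 0.30 = 0.44; 0.20 + 0.80 × 0.45 = 0.56; 0.56 / 0.44 = 1.27.

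If the TEAE filter caught every unchanged background symptom, the inflation would be zero.

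**3. What a pre-dose score would recover.** Count only new or worsened symptoms. Let w be the share of drug effects in already symptomatic subjects that raise their score. Then:

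rate = (1 − b)q + wbq

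At b = 20% and true rates 30% vs 45%:

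- w = 0: 24.0% vs 36.0%, difference 12.0 points, ratio 1.50.
- w = 0.5: 27.0% vs 40.5%, difference 13.5 points, ratio 1.50.
- w = 1: 30.0% vs 45.0%, difference 15.0 points, ratio 1.50.

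The inflation disappears and the ratio is restored in every case. The risk difference returns only as far as already symptomatic subjects get worse.

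**The case against.** The strongest case on the other side is that the plan already guards against this. Section 8.6 requires an AE, not a TEAE, and the TEAE definition excludes unchanged symptoms. History, indication, prior medication and AEs from consent all give pre-dose information. Investigators grade the intensity and causality of each AE, and SAP 3.2.2.1 tabulates related TEAEs separately. Exclusion criterion 13 removes subjects prone to nausea or vomiting, and criterion 2 removes moderate to severe active inflammatory bowel disease. Several passages confine the rating to effects of the preparation.

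Most of this stands as a limit on the point. A reader might infer that TEAE rates are certain to be inflated, or that the analyst has no pre-dose information at all. The documents support neither. What is missing is a rating on the same scale, so the filter works only where a site happens to have recorded a comparable symptom. Cramping and bloating have no exclusion like the one for nausea. The attribution wording does not settle the matter either, because the AE trigger sits in 8.6, which asks about overall experience.

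A reader might also infer a false difference between arms. Randomisation balances background symptoms on average, so none is expected. The AE and symptom analyses are descriptive, and no hypothesis test rests on them.

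**Conclusion.** The point holds in a limited form. As written, 8.6 can make an unchanged background symptom an AE contrary to 8.1.1, and the worsening criterion for TEAEs cannot be applied reliably to cramping, bloating and nausea. TEAE rates in both arms may therefore be too high, and their ratio too close to 1.

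The size cannot be derived from the documents. The table in the working rests on assumed rates, equal background in both arms, independence from the drug effect and no filtering. It shows direction, not an estimate. The primary endpoint is unaffected.

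It would also be too strong to say that a pre-dose score recovers the whole lost difference: it corrects the absolute rates and the ratio, and the difference only in part. This is a cheap improvement to a secondary comparison, not a threat to the trial's main conclusion.

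**What to change.** 1. Add the same three items to the leaflet, to be rated immediately before Dose 1.
2. Reconcile Protocol 8.6 with 8.1.1, 3.2.2.2, the synopsis and SAP 1.4.2.2. Use one description of what is rated, and report a score of 2 or more as an AE when the symptom is new or scored higher than before Dose 1.
3. In SAP 3.2.2.4, show by arm the proportion new or worsened and the change from the pre-dose score, alongside the raw scores.
4. For subjects already enrolled, add a sensitivity table of TEAEs. Leave out these three symptoms where they match ongoing medical history, the indication for colonoscopy or a pre-dose AE and no worsening was recorded. This may remove some true worsening that nobody documented, so present it beside the main table and not in its place.

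The cost is three extra ratings, an eCRF update, SAP wording and a slightly more complex reporting rule for sites. Timing matters. The current protocol is dated 02 March 2020 with a planned end in Q2 2020, and SAP version 4.0 is dated 25 August 2020. The leaflet change may reach few or no subjects in this trial, in which case item 4 is the practical remedy.

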# 9 ASSESSMENTS OF PHARMACOKINETICS/PHARMACODYNAMICS

Pharmacokinetics and pharmacodynamics are not assessed in this study.

PAGE 56/103

#### 10 STATISTICS

# **10.1** Analyses Populations

The following population will be used during statistical analyses:

- Screened population: All subjects screened (i.e. who signed the informed consent).
- Safety population: All randomised subjects with at least a partial dose of study medication. Subjects will be assessed according to the treatment received.
- **Intention to treat (ITT) population**: All randomised subjects who received even a partial dose of study drug. Subjects will be assessed according to their randomised treatment, regardless of the treatment they receive.
- Modified Intention to treat Analysis Set (mITT): All randomised subjects who received even a partial dose of study treatment and produced a primary efficacy assessment.
- **Per protocol (PP) population**: All subjects in the ITT population, who have undergone the colonoscopy procedure and for whom no major protocol violations/deviations occurred.

# 10.1.1 Populations Analysed

The primary analysis based on the primary efficacy endpoint will be performed on the mITT population. In that analysis, subjects who do not undergo colonoscopy because of inadequate preparation or preparation-related AEs will be considered as failures. In addition, robustness of primary efficacy results will be assessed by repeating the primary analysis on the PP population. The analyses of safety data will be performed based on the safety population.

# 10.1.2 Subject Allocation and Reasons for Exclusion from the Analyses

Any major protocol deviation will be described in the Protocol Deviation Document (PDD) and its impact on inclusion in each analysis population (mITT/PP population) for any subject will be specified. The final list of protocol deviations impacting the mITT/PP population will be reviewed during the data review meeting held prior to database lock. The list will be updated to include any additional major protocol deviations impacting inclusion in the PP population.

# **10.2** Sample Size Determination

The primary aim of the study is to show that Eziclen®/Izinova® is not inferior to Klean-Prep® in the proportion of subjects with successful colon cleansing.

A non-inferiority margin of 15% has been selected for consistency with other studies in colon cleansing preparations.

Therefore assuming a success rate (excellent or good response) of 85% in both the Eziclen®/Izinova® and Klean-Prep® groups, a one-sided alpha of 0.025 and 90% power, 120 subjects are required per treatment group. Assuming a rate dropout/non-compliance to protocol of 4% based on previous studies and taking into account that subjects will be hospitalised for treatment administration, 125 subjects will be randomised in each treatment group, i.e. 250 subjects in total. Enrolment will be completed once 250 subjects have been randomised.

The primary endpoint of treatment success will be tested sequentially (hierarchical structure) with the first test being non-inferiority test based upon the treatment difference. A rejection of the null hypothesis will trigger superiority testing based upon the treatment difference.

